## 7.3. Method of Treatment Assignment and Blinding

Patients will be randomized in a 1:2:1 ratio (12 mg BID:8 mg BID:placebo). Randomization will be stratified by scalp hair loss into one of the following two categories: 1) Partial scalp hair loss (SALT  $\geq$  50 and < 95); 2) Complete or near-complete scalp hair loss (SALT  $\geq$  95). The randomization schedule will be generated prior to study start.

All study patients, Investigators, and site study staff will be blinded to study drug assignment for the duration of the study. Tablets and packaging of CTP-543 and placebo will be identical in appearance.

## 7.4. Rationale for Study Design, Doses, and Primary Endpoint

Double-blind, randomized, placebo-controlled studies are considered optimal for obtaining unbiased estimates of the efficacy and safety of investigational products. The Severity of Alopecia Tool (SALT) (Olsen, 2004) was introduced as part of investigative guidelines published by the National Alopecia Areata Foundation is widely used to assess the extent of the scalp surface hair loss in AA. The SALT has been used as the hair loss measurement scale in all the studies of CTP-543 in patients with alopecia areata to date. The 24-week duration of the Treatment Period has been shown to be sufficient in establishing hair regrowth with CTP-543 and to significantly differentiate active doses from placebo as well as differentiate between doses of CTP-543.

The selection of the 8 mg and 12 mg BID doses of CTP-543 for this study is supported by the efficacy and safety of CTP-543 observed in the completed and analyzed Phase 2 CP543.2001, CP543.2002, and CP543.2003 studies. Analysis of the primary efficacy endpoint in CP543.2001 showed that the proportions of responders (patients achieving at least a 50% relative reduction in SALT score from Baseline at Week 24) were significantly greater in the 8 mg BID group and 12 mg BID group compared with the placebo group (P < 0.001 for both) and compared with the 4 mg BID group (P = 0.030 and P = 0.003, respectively). For the analysis performed on the efficacy population, 9.3% of patients in the placebo group and 21.4% of patients in the 4 mg BID

group were responders, compared with 47.4% in the 8 mg BID group and 58.3% in the 12 mg BID group. Results also showed a significantly greater proportion of responders in the 8 mg BID and 12 mg BID groups which had at least 50%, 75%, and 90% relative reduction in SALT score by Week 24 compared with both the placebo group and the 4 mg BID group.

Additionally, both the 8 mg BID group and the 12 mg BID group had significantly greater proportions of patients who achieved an absolute SALT score  $\leq$ 20 at Week 24 compared with the placebo group. Achieving a SALT score  $\leq$  20 has been reported by AA patients and clinicians to represent clinically-meaningful treatment success for AA (Wyrwich, 2020). In the Wyrwich study, qualitative interviews were conducted in the US with hair expert dermatologists and AA patients who had experienced  $\geq$ 50% scalp hair loss. The clinicians judged that 80% scalp hair represented treatment success. Adult and adolescent AA patients participating in the study perceived that, short of 100% scalp hair, the presence of  $\sim$ 70-90% scalp hair (median 80%) represented treatment success. Nearly all queried clinicians and patients in this study agreed that for patients with  $\geq$  50% scalp hair loss, successful treatment would be hair regrowth resulting in  $\leq$  20% scalp hair loss.

Therefore, based on the efficacy and safety data observed in the CP543.2001, CP543.2002, and CP543.2003 studies, 8 mg BID and 12 mg BID of CTP-543 will be assessed further for efficacy and safety in the Phase 3 program in patients with moderate to severe alopecia areata. This Phase 3 study will employ SALT as the hair loss assessment tool and the primary efficacy endpoint will be the percentage of patients who achieve a SALT score ≤ 20, as this represents a clinically-meaningful treatment success for patients with AA. This same primary endpoint is currently being used in the ongoing Phase 3 study, CP543.3001.

**Table 2:** Schedule of Assessments

|   | Screening                                   | Baseline/
Randomization   | Treatment Period  |                                  |    |                          | Safety
Follow-Up                |
|---|---|------------------------------|-------------------------------|----------------------------------|----|--------------------------|------------------------------------|
|   | Day -28 to Day -1 
(Visit 1) | Day 1  (Visit 2) | Week 2
(Visit 3)           | Week 4, 8, 12
(Visit 4, 5, 6) |    | Week 24
(Visit 9)/ ET | Week 28
(Visit 10)  |
| Event  Informed consent   | X   |                              |                               |                                  |    | Visit                    |                                    |
| Eligibility assessment  | X   | X                            |                               |                                  |    |                          |                                    |
| Demographics  | X   | Λ                            |                               |                                  |    |                          |                                    |
| Medical history   | X   | X                            |                               |                                  |    |                          |                                    |
| Randomization   | A   | X                            |                               |                                  |    |                          |                                    |
| Complete physical examination   | X   | X                            |                               |                                  |    | X                        | Х                                  |
| Brief physical examination  | A   | A                            |                               | X                                | X  | Α                        | 74                                 |
| Height  | X   |                              |                               | 71                               | 71 |                          |                                    |
| Weight  | X   | X                            |                               | X                                | X  | X                        | X                                  |
| Pregnancy test    | X   | X                            |                               | X                                | X  | X                        | X                                  |
| Tuberculosis test   | X   |                              |                               |                                  |    |                          |                                    |
| Clinical laboratory testing   | X                               | X                            | $X^{10}$                      | X                                | X  | X                        | X                                  |
| Pharmacokinetic Sampling for Population Pharmacokinetics                            |   | X                            |                               | X                   |    | X                        |                                    |
| HBV and HCV test  | X   |                              |                               |                                  |    |                          |                                    |
| 12-lead electrocardiogram   | X   |                              |                               | $X^{12}$                         |    | X                        |                                    |
| Vital signs   | X   | X                            |                               | X                                | X  | X                        | X                                  |
| Severity of Alopecia Tool assessment                                   | X   | X                            |                               | X                                | X  | X                        |                                    |
| Photographs of the scalp  | X   | X                            |                               | X                                | X  | X                        |                                    |
| Photographs of eyebrows, eyelashes, and hands                                       |   | X                            |                               | X                   |    | X                        |                                    |
| Eyebrow Assessment (BETA)   |   | X                            |                               | X                   |    | X                        |                                    |
| Eyelash Assessment (BELA)   |   | X                            |                               | X                   |    | X                        |                                    |
| Patient Reported Outcome Scales: SPRO and QPRO                                      |   | X                            |                               | X                   | X  | X                        |                                    |
| Patient and Clinical Global Impression of Improvement (PGI-I, CGI-I  ) |   |                              |                               | X                   | X  | X                        |                                    |
| Patient and Clinical Global Impression of Severity (PGI-S, CGI-S  )    |   | X                            |                               | X                   | X  | X                        |                                    |
| Hospital Anxiety and Depression Scale (HADS)  |   | X                            |                               |                                  |    | X                        |                                    |
| Dispense study drug    |   | X                            |                               | X                                | X  |                          |                                    |
| Study drug accountability   |   |                              |                               | X                                | X  | X                        |                                    |
| Adverse events   | X   | X                            | X                             | X                                | X  | X                        | X                                  |
| Concomitant medications    | X   | X                            | X                             | X                                | X  | X                        | X                                  |

## HBV = hepatitis B virus; HCV = hepatitis C virus

 Due to the COVID-19 pandemic, patient study visits may be performed remotely when the provider and patient are not able to be physically present in the clinic. Study personnel should strive to perform assessments per the schedule of events above with the understanding that all assessments may not be able to be performed (ECGs, vitals, SALT assessments).

-  Randomization/Day 1 may occur any time after eligibility has been confirmed.
- $^3$  All subsequent visits and week increments should be based on the date of Visit 2 (Day 1).  $^4$  All visit windows are  $\pm 2$  days.
-  The Safety Follow-Up Visit is intended for those patients who do not roll over into the Open-Label Extension.

 For females of childbearing potential, a serum pregnancy test will be performed at Screening. Throughout the Treatment Period, and at the safety follow-up (if applicable), urine pregnancy tests will be performed.

 Includes fasted hematology, serum chemistry, and lipids performed by the central lab.

8 Collected pre-dose.

-  Will include thyroid stimulating hormone and hemoglobin A1c at Screening only.
-  Will include hematology and serum chemistry **only**.
-  Should be performed by the same rater for the patient for the duration of the study.
-  Performed at Week 12 only.
-  Due to COVID-19, Site to Subject (STS) or Direct to Subject (DTS) shipping services may be warranted in cases where a patient is not able to attend in clinic visits or a site is closed.
-  Collection is ongoing.

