## **Duration of study participation:**

Upon completion of the 24-week Treatment Period, patients will be eligible to either enroll in the Open-Label Extension study or complete treatment and exit the study following the 4-week Safety Follow-up visit. Patients will participate in the study for up to 32 weeks if they decide not to enroll in the Open-Label Extension study (4-week Screening, 24-week Treatment, 4-week Safety Follow-up). Otherwise study duration will be up to approximately 28 weeks.

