## 7. OVERALL STUDY DESIGN

## 7.1. Study Design

This is a double-blind, randomized, placebo-controlled, multicenter study to evaluate the efficacy and safety of CTP-543 in adult patients with moderate to severe alopecia areata. Patients will require a definitive diagnosis of alopecia areata by the Investigator based on clinical evaluation involving physical examination and medical history. The patient's alopecia areata will be classified by the Investigator into one of two categories defined for this study:

[figure not shown]
- 1) Partial scalp hair loss (SALT score  $\geq$  50 and < 95);
- 2) Complete or near-complete scalp hair loss (SALT  $\geq$  95).

Patients will be between 18 and 65 years of age and experiencing a current episode of hair loss associated alopecia areata lasting at least 6 months and not exceeding 10 years. Total disease duration may exceed the duration of the current episode. Patients will require at least 50% hair loss as measured by the SALT assessment at Screening and Baseline, and should not be treated concurrently for alopecia areata or with other treatments that might affect hair regrowth.

An independent Data Monitoring Committee (DMC) will perform regular safety assessments. The DMC will convene to review accumulated safety data at regular intervals specified in the DMC Charter. The DMC will determine if there are adequate safety data to support continuation of a particular dose group or individual patient and may advise study and/or treatment arm cessation due to intolerability at any time.

The Screening Period may last up to 28 days prior to initiation of study drug. The Treatment Period is a 24-week, double-blind, placebo-controlled period to define efficacy and safety for CTP-543. Following the 24-week Treatment Period, patients will have the opportunity to continue receiving treatment in an Open-Label Extension study. If a patient does not wish to continue into the Open-Label Extension study, they will complete treatment at Week 24 and return in 4 weeks for the Post-Treatment Safety Follow-up to assess safety following treatment completion.

Figure 1: Study Design

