#### **Adverse Events**

An adverse event reported after informed consent, but before the first dose of study drug (i.e., Day 1), will be considered a pre-treatment adverse event. Treatment-emergent adverse events (TEAEs) will be defined as any adverse event that occurs after administration of the first dose of study drug through to the final study visit. The number and percentage of patients who report TEAEs will be summarized by system organ class and preferred term.

Treatment emergent adverse events will also be summarized by intensity as well as relationship to study drug.

Patients who report the same preferred term on multiple occasions will be counted once for the preferred term: under the highest severity when summarized by severity and under the closest relationship to study drug when summarized by relationship. If a patient reports multiple preferred terms for a system organ class, the patient will be counted only once for that system organ class.

Proportions for adverse events that are gender-specific (e.g., dysmenorrhea) will be based on the number of patients from that gender.

The number and percentage of patients who experience TEAEs will be summarized by treatment group for the following:

- By system organ class and preferred term
- By severity/intensity, system organ class, and preferred term
- By relationship to study drug, system organ class, and preferred term
- Serious adverse events by system organ class and preferred term
- Serious adverse events by relationship to study drug, system organ class, and preferred term
- Adverse events resulting in discontinuation of study drug by system organ class and preferred term
- Adverse events that result in study drug dose interruption by system organ class and preferred term

By-patient listings will be provided for any deaths, serious adverse events, and adverse events leading to discontinuation of treatment. Treatment-emergent adverse events that result in dose interruption will also be identified.

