#### 9.3. Adverse Events

An adverse event is any untoward medical occurrence that may appear or worsen in a patient during the course of a study. It may be a new intercurrent illness, a worsening concomitant illness, an injury, or any concomitant impairment of the patient's health, including laboratory test values, regardless of etiology. Any worsening (ie, any clinically significant adverse change in the frequency or intensity of a pre-existing condition) should be considered an adverse event. A diagnosis or syndrome should be recorded on the adverse event page of the eCRF rather than the individual signs or symptoms of the diagnosis or syndrome. A worsening of the condition under study, alopecia areata, will not be reported as an adverse event.

All patients will be monitored for adverse events during the study. Assessments may include monitoring of the following parameters: the patient's clinical symptoms, laboratory, physical examination findings, or findings from other tests and/or procedures.

Adverse events will be coded using MedDRA version 23.1 and summarized by treatment group, system organ class, and preferred term.

An adverse event reported after informed consent, but before the first dose of study drug (i.e., Day 1), will be considered a pre-treatment adverse event. Treatment-emergent adverse events will be defined as any adverse event that occurs after administration of the first dose of study drug. Adverse events will be limited to those collected within this protocol (ie, for rollover subjects, AEs collected under the protocol of the rollover study will not be in this study). The number and percentage of patients who report TEAEs will be summarized by treatment group, system organ class, and preferred term.

Treatment emergent adverse events will also be summarized by intensity as well as relationship to study drug.

Partial dates will be imputed for the purposes of defining TEAEs as follows:

- For a missing start day where the month and year are present, the start day will be set to the first day of the month, unless 1) the first day of the month is before the date of administration of study drug and the month and year are the same as the month and year of the date of administration of study drug, and 2) the end date is on or after the date of administration of study drug or the end date is completely missing, in which case the start day will be set to the first day of administration of study drug.

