#### 9.5. Clinical Laboratory Evaluation

Clinical laboratory samples should be collected at the beginning of each clinic visit and just prior to a dose on all Study Visit Days and will be processed by a central laboratory. In the event a patient is unable to attend an in-clinic visit due to COVID-19, clinical laboratory blood draws may be performed by a Home Health Care agency or a local laboratory.

Clinical laboratory variables will be presented in 4 ways. First, change from baseline to the minimum post-baseline value, maximum post-baseline value, and final value will be summarized. Baseline will be defined as the laboratory value obtained before the first dose of study drug on Day 1; if Day 1 values are unavailable, then values obtained at the Screening Visit will be used. Only post-baseline values on treatment will be eligible. The Follow-up Visit will be excluded from possible minimum, maximum, or final post-baseline values.

This analysis will be repeated with outlying values removed from eligibility for minimum and maximum values. An outlier is defined using the interquartile range (IQR). The IQR is equal to the third quartile minus the first quartile and will be calculated by visit and treatment group for each numeric parameter. The IQR will be multiplied by a constant of 1.5. Any value which is above 1.5 times IQR plus the third quartile or below 1.5 times IQR minus the first quartile will be considered an outlier and will be removed from eligibility for minimum, maximum, or final post-baseline values.

Second, shift tables will summarize by treatment group and active overall the number and percentage of patients with categorical changes from baseline defined by the laboratory normal reference range for each laboratory parameter (Below reference range, Within reference range, and Above reference range). The baseline category will be cross-tabulated with post-baseline category ( $3 \times 3$  table). The post baseline category will be assigned and summarized in 2 ways for each laboratory parameter: minimum post-baseline value and maximum post-baseline value. Only post-baseline values on treatment will be eligible. Patients will only be reported in the shift tables if they have both a baseline and post-baseline value.

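### Among Week 24 completers, adverse events are counted for about four extra off-drug weeks only in those who decline the extension, so the overall TEAE tables compare unequal windows if the declining share differs by arm

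*Protocol*

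**What the plan says.** **Who is seen at Week 28.** Protocol Table 2 schedules adverse event collection at Week 28, and its footnote 5 says "The Safety Follow-Up Visit is intended for those patients who do not roll over into the Open-Label Extension". Protocol 7.1 says of patients who do not continue that "they will complete treatment at Week 24 and return in 4 weeks for the Post-Treatment Safety Follow-up", so the extra weeks are off drug.

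**Length of participation.** The Protocol synopsis states: "Patients will participate in the study for up to 32 weeks if they decide not to enroll in the Open-Label Extension study". For everyone else: "Otherwise study duration will be up to approximately 28 weeks". Both figures include a screening period of up to four weeks.

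**What counts as treatment-emergent.** Protocol 12.4.8 counts "any adverse event that occurs after administration of the first dose of study drug through to the final study visit". SAP 9.3 states no end: "Treatment-emergent adverse events will be defined as any adverse event that occurs after administration of the first dose of study drug". It adds that "for rollover subjects, AEs collected under the protocol of the rollover study will not be in this study". SAP section 13, which lists changes from the protocol, does not mention the dropped end point. SAP section 2 gives the SAP precedence where the two documents differ.

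**Denominator.** SAP section 13 bases adverse event proportions on the Safety Population. SAP 9.3 plans no exposure-adjusted rate.

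**Related rules.** Protocol 12.4.8 and SAP 9.3 also plan treatment-emergent tables by arm for weeks 0 to 12 and 12 to 24. For laboratory extremes, SAP 9.5 says "The Follow-up Visit will be excluded from possible minimum, maximum, or final post-baseline values". No matching limit is stated for adverse events.

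**The concern.** For a patient who completes 24 weeks, the end of the counting window depends on a choice made after randomisation: enter the extension or not. That choice may depend on response and tolerability, and so on arm. Protocol 12.1 assumes Week 24 response of 40%, 26% and 9% on 12 mg, 8 mg and placebo, so a difference in willingness to continue is plausible.

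If the declining share differs, part of a between-arm difference in crude percentages reflects length of observation and not risk. Safety is a primary objective (Protocol 6.1), and these tables are its main comparative output. A second consequence is internal: an event with onset after Week 24 enters the overall tables but belongs to neither planned interval, so the two sets of tables may not reconcile.

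**Working it through.** **1. Reproduce the plan's durations.** With follow-up: 4 + 24 + 4 = 32 weeks. With rollover: 4 + 24 = 28 weeks. Both match the synopsis. Removing the four screening weeks leaves about 28 and 24 weeks after first dose. The difference is 4 weeks, or 4/24 = 16.7% more observation, all of it off drug.

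**2. Set the rules side by side.**

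| Patient | Events counted up to |
|---|---|
| Completes Week 24, enters the extension | about Week 24; later events belong to the other study |
| Completes Week 24, declines the extension | about Week 28 |
| Withdraws consent early | early termination visit, plus a safety follow-up as appropriate (Protocol 9.2.1) |

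All three are in the same denominator.

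**3. Size among completers.** Assume that every patient reaches Week 24, and that the event rate is constant and equal in all arms. Let p24 be the 24-week incidence and g the between-arm gap in the share declining the extension. Then

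- p28 = 1 − (1 − p24)^(28/24)
- spurious difference = g × (p28 − p24)

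The documents give neither g nor p24, so both are assumed.

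| p24 | p28 | p28 − p24 | g = 10 points | g = 20 points | g = 30 points |
|---|---|---|---|---|---|
| 10% | 11.57% | 1.57 points | 0.16 | 0.31 | 0.47 |
| 30% | 34.04% | 4.04 points | 0.40 | 0.81 | 1.21 |

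With g = 0 the distortion is zero. With 10% declining in one arm and 30% in another, mean observation is 24 + 4 × 0.10 = 24.4 weeks against 24 + 4 × 0.30 = 25.2 weeks.

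**4. Sensitivity to the off-drug event rate.** If the rate doubled in the four off-drug weeks (assumed), a 20-point gap would give 0.62 points at 10% incidence, 1.57 at 30% and 2.11 at 60%.

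**5. Early withdrawals.** A patient who withdraws at Week 8 and has a follow-up four weeks later contributes about 12 weeks, which is 12 fewer than a rollover completer. A declining completer contributes 4 more. One such withdrawal therefore offsets the extra time of 12/4 = 3 declining completers. An arm with fewer rollovers can have more or less observation time, depending on why its patients did not roll over.

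**6. Scale.** One patient in an arm of 110 is 1/110 = 0.9 points. The standard error of a difference between two arms of 110 is √(2 × 0.10 × 0.90/110) = 4.0 points at 10% and √(2 × 0.30 × 0.70/110) = 6.2 points at 30%. The upper ends in step 3 are 0.47/4.0 = 0.12 and 1.21/6.2 = 0.20 of one standard error.

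**The case against.** The case against acting has four parts.

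- **A common-window view is already planned.** The 0-12 and 12-24 week incidence tables count only onsets within the interval, by arm, among patients dosed in it. SAP 6.1 also reports extension enrolment by arm, so an imbalance would be visible. This stands. It confines the problem to the overall tables by class and term, severity, relationship and seriousness.
- **The effect is small and nothing is tested.** Safety summaries are descriptive (SAP 9.1), and the calculated distortion is a fraction of one standard error. This stands, and it sets the priority. It does not justify leaving a known asymmetry that is cheap to remove.
- **Counting to the final visit is a legitimate protocol choice.** It keeps events arising soon after the last dose in the main table, and some of these could be delayed or withdrawal effects of the drug. This stands in part: such events should stay visible by arm, and the fix must provide for that.
- **A Week 24 cut does not equalise everything.** Patients who stop drug early are followed off drug to Week 24 (Protocol 8.3), and withdrawals still have shorter windows. This stands. The cut removes only the asymmetry created by the visit schedule.

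A reader might also infer that the arm with fewer rollovers will look worse. The documents do not support this. It holds only if non-rollover patients are mainly completers who decline the extension, and step 5 shows how withdrawals can offset or reverse it.

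**Conclusion.** The point holds in conditional form, as a minor improvement. Completers are observed for about 24 or 28 weeks after first dose according to whether they enter the extension, and the overall tables do not adjust for it. If the declining share differs by arm, the distortion is about 0.2-0.5 points at 10% 24-week incidence and 0.4-1.2 points at 30%. These figures rest on assumed gaps of 10 to 30 points among completers and a constant event rate equal across arms. With equal declining shares this source of distortion is zero. No test or alpha level is affected.

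Two further inferences go too far. One is that the plan offers no comparison over a common period; the interval tables provide one for the onsets they cover. The other is that events after Week 24 are unrelated to the drug; nothing in the documents shows this.

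**What to change.** In SAP 9.3, base the between-arm TEAE and serious-event tables on onset from first dose through the Week 24 visit, or the last visit if earlier. Show events with later onset in an adjacent follow-up table by arm, with the patients who entered follow-up as denominator. Keep all events in the listings. Record the change from Protocol 12.4.8 in SAP section 13.

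This aligns with the exclusion of the Follow-up Visit in SAP 9.5. It is not the same as that section's on-treatment rule, because off-drug events before Week 24 would still count.

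The cost is one sentence in 9.3, a line in section 13 and one table. A few post-treatment events, some possibly drug-related, move from the main table to the one beside it. Off-drug time before Week 24 in early discontinuers, and shorter follow-up in withdrawals, remain.
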